Telemetry	X				X								Telemetry only required for doses > 200 mg and must start at least 60 min pre-dose and be continuous for 24h post-dose. See Section 8.2.5.
Holter monitoring	X				X		X		X				Holter monitoring must start at least 60 min pre-dose and be continuous for 24h post-dose.
12-lead ECG (Triplicate)	X	X	X		X		X		X	Q1W	X		On serial PK days (Day 1, 8 and 15), triplicate ECGs will be obtained at or about the time of each PK sample collection, as described in the SRM. On other days, triplicate ECGs will be obtained pre-dose.
Laboratory Assessments (Safety) – perform assessments pre-dose on each dosing day													
Clinical Chemistry, Urinalysis and Coagulations	X				X		X		X	Q1W	X		Refer to Appendix 2 for complete list of required laboratory assessments.
Hematology	X			X	X	X	X		X	Q1W	X		Hematology twice per week for the first two weeks (see Section 2.3.1). Refer to Appendix 2 for complete list of required laboratory assessments.
Pregnancy test					X				X	Q4W	X		Perform only in women of child bearing potential (WOCBP). Pregnancy tests during intervention phase and at discontinuation may be either serum

Procedure	DLT period (Days 1-21) ³								D22 ³	Continuation ³	TDV ¹	Follow-up	Notes		
	D1 ²	D2	D3	D4	D8	D11	D15	D16							
													or urine. Final pregnancy test must be performed within 150 days after last study intervention.		
Study intervention															
Administer study drug	X			←=====Daily Dosing=====→											A dose will be administered on Day 1, no dose will be given on Day 2 or Day 3 of the first cycle, after which, daily dosing will occur through the remainder of cycle 1 and all subsequent cycles. GSK3368715 should be administered in a fasted state at approximately the same time of day (\pm 4 h), with no food for 1 hour before and 2 hours after each dose. See Section 5.3.1 for dosing instructions on serial PK days.
Efficacy Assessment															
Tumor Imaging. Must include CT Chest. Must include CT abdomen if history of documented intraabdominal disease.										Week 9 Day1 then every 8 weeks until Week 33 Day 1 and then Q16W	X		Disease assessments will be performed until disease progression. Participants who discontinue for reasons other than PD will also be followed until the start of subsequent anti-cancer intervention. CR or PR should be confirmed as per response criteria in Appendix 10 .		
Patient Reported Outcomes															

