Telephone interview (Part 2 only)										Week 9	X		Qualitative telephone interview to be completed within 21 days following the week 9 disease assessment and then again following the TDV. Participants who have the TDV within 30 days of the week 8 interview are not required to repeat the interview		
Follow-up for Survival												Q12W	Participants will be followed every 12 weeks for survival and subsequent anti-cancer therapy. The survival follow-up visit will commence after discontinuation of study treatment. Participants should be contacted every 12 weeks (\pm 2 weeks)		

Procedure	DLT period (Days 1-21) ³								D22 ³	Continuation ³	TDV ¹	Follow-up	Notes
	D1 ²	D2	D3	D4	D8	D11	D15	D16					
													until death, termination of the study or participant has been followed for 2 years.
Tumor Specimens													
Tumor biopsy (Optional unless participant is in PK/PD cohort, see Table 3 below)									(X)				On intervention biopsies are optional (unless medically indicated) for individual participant(s)
Pharmacokinetics (PK), Pharmacodynamics (PD) and Pharmacogenomics (Genomics Research)													
PK plasma samples (parent drug and metabolites profiling for participants are in PK/PD cohort, see Table 3 below).	X	X	X	X	X			X	X	X	Q4W		On Day 1, patients will be administered GSK3368715 as a single oral dose followed by a 72 h intervention-free period to evaluate PK of the parent compound and its metabolites in plasma samples. Plasma metabolites will be analyzed at the timepoints indicated in Table 3 below. PK samples following Day 1 dose will be collected at Pre-dose, 15 ± 5 min, 30 ± 5 min, 1h ± 5 min, 1.5h ± 5 min, 2h ± 10 min, 3h ± 10 min, 4h ± 10 min, 6h ± 30 min, 8h ± 30 min, 12h ± 2h, 24h ± 2h, 48h ± 2h, 72h ± 2 hrs post-dose. The 48 hr and 72 hr timepoints could be removed with emerging data. PK samples on Day 8 will be collected at Pre-dose, 1.h ± 5 min and 4h ± 10 min. PK samples on Day 15 will be collected at Pre-dose, 30 ± 5 min, 1h ± 5 min, 2h ± 10 min, 3h ± 10 min, 4h ± 10 min, 6h ± 30 min, 8h ± 30 min, 12h ± 2h, 24h ± 2h (prior to next dose) post-dose. On Day 22) and then every 4 weeks during the continuation phase, only pre-dose PK samples should be collected. All pre-dose PK samples should be collected within 2h prior to the dose being administered.
Plasma for circulating free	X				X			X		X			Plasma for circulating free MMA, ADMA and/or SDMA will be collected pre-dose on Day 1 and 4h

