2.2.1.5. Clinical Pharmacology of GSK3368715

Pharmacokinetics (PK) of GSK3368715 is currently being evaluated after administration of single and repeat daily oral administration of GSK3368715 at doses of 50mg to 200mg in study 207675. Concentrations are detected in plasma 0.25 hours after oral administration with peak concentrations at around 1.0 hours on average, then GSK3368715 declines bi-exponentially with a mean terminal elimination half-life of 20-24 hours. A dose dependent increase in plasma exposures (both C_{max} and AUC) of GSK3368715 were observed as doses increased from 50mg QD to 200 mg QD. Following multiple-dose administration, mean AUC was up to 2-4 fold higher on Day 15 as compared to Day 1 in all dose groups, except for participants ^{PPD} and ^{PPD} who showed much higher accumulation on Day 15 of 6-7 folds relative to Day 1.

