8.6. Pharmacokinetics

All participants enrolled in Part 1 (dose escalation/food effect) will receive a single dose on Day 1 and then begin continuous dosing after collection of the 72 hour PK sample. The timing of the PK samples may be altered and/or additional PK samples may be obtained at additional points to ensure thorough monitoring.

For details of PK sample collection, please refer to Section 1, [Table 2](#).

Day 1: participants will be administered GSK3368715 as a single oral dose followed by a 72 hour intervention-free period to evaluate PK. PK samples following Day 1 dose will be collected at Pre-dose, 15 ± 5 min, 30 ± 5 min, 1h ± 5 min, 1.5h ± 5 min, 2h ± 10 min, 3h ± 10 min, 4h ± 10 min, 6h ± 30 min, 8h ± 30 min, 12 ± 2h, 24 ± 2h, 48 ± 2h, 72 ± 2 hrs post-dose.

Day 8: PK samples will be collected at Pre-dose, 1.0h ± 5 min, and 4h ± 10 min post-dose.

Day 15: PK samples will be collected at Pre-dose, 30 ± 5 min, 1h ± 5 min, 2h ± 10 min, 3h ± 10 min, 4h ± 10 min, 6h ± 30 min, 8h ± 30 min, 12 ± 2h, and 24 ± 2h (prior to the next dose) post-dose.

PK samples on other visit days should be collected pre-dose only. All pre-dose PK samples at each visit should be collected within 1 hour prior to dose administration.

For details of PK sample collection for the PK/PD cohort in Part 1, please refer to Section 1.3, [Table 3](#).

For details of PK sample collection during the food effect cohort in Part 1, please refer to Section 1.3, [Table 4](#).

Meal times will be recorded on all PK collection days for Part 1 (dose escalation and PK/PD cohort) and on the dosing days (Days 1 and 5) in the food effect cohort.

Whole blood samples of approximately 2 mL will be collected for measurement of GSK3368715 and its metabolites as specified in the SoA. Blood may be collected at additional time points during the study if warranted and agreed upon between the investigator and the sponsor. Instructions for the collection and handling of biological samples will be provided by the sponsor. The actual date and time (24-hour clock time) of each sample will be recorded. Details of PK blood sample collection, processing, storage and shipping, procedures will be provided in study reference manual (SRM).

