**Table 2 Derived Pharmacokinetic Parameters**

| Parameter | Parameter Description  |
|------------------|---|
| $C_{\max}$       | Maximum observed concentration; determined directly from the concentration-time curve.  |
| $T_{\max}$       | Time from first administration to occurrence of $C_{\max}$ ; determined directly from the concentration-time curve.   |
| $C_{\tau}$       | Also referred to as “ $C_{\text{trough}}$ ”; observed concentration at the end of a dosing interval, immediately before the next administration; determined directly from the concentration-time curve.   |
| AUC(0-t)         | Area under the concentration-time curve from time zero to the time of the last quantifiable concentration (C(t)) will be calculated using the linear trapezoidal rule for each incremental trapezoid and the log trapezoidal rule for each decremental trapezoid. |
| AUC(0-∞)         | Area under the concentration-time curve extrapolated to infinity will be calculated as:

$AUC = AUC(0-t) + C(t) / \lambda_z$
This will be calculated for Week 1/Day 1 only   |
| AUC(0-τ)         | Area under the concentration-time curve from time zero to the predose of the next dose.   |
| $\lambda_z$      | Apparent terminal phase elimination rate constant   |
| $t_{1/2}$        | Apparent terminal half-life will be calculated as:

$t_{1/2} = \ln 2 / \lambda_z$   |
| TI               | Time invariance

$TI = \frac{AUC(0 - \tau), Day15}{AUC(0 - \infty), Day1}$  |
| AR               | Accumulation ratio

$AR = \frac{AUC(0 - \tau), Day15}{AUC(0 - \tau), Day1}$   |
| RCMAXM1          | Metabolite to drug Cmax ratio

$RCMAXM1 = (C_{\max} \text{ of GSK3963583} * MW \text{ of GSK3368715}) / (C_{\max} \text{ of GSK3368715} * MW \text{ of GSK396358})$   |

| Parameter | Parameter Description   |
|-----------|---|
| RCMAXM2   | Metabolite to drug Cmax ratio

$RCMAXM2 = (C_{max} \text{ of GSK3983164} * MW \text{ of GSK3368715}) / (C_{max} \text{ of GSK3368715} * MW \text{ of GSK3983164})$      |
| RAUCM1    | Metabolite to drug AUC(0-t) ratio

$RAUCM1 = (AUC(0-t) \text{ of GSK3963583} * MW \text{ of GSK3368715}) / (AUC(0-t) \text{ of GSK3368715} * MW \text{ of GSK396358})$  |
| RAUCM2    | Metabolite to drug AUC(0-t) ratio

$RAUCM2 = (AUC(0-t) \text{ of GSK3983164} * MW \text{ of GSK3368715}) / (AUC(0-t) \text{ of GSK3368715} * MW \text{ of GSK3983164})$ |

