The parameters which involve derivation of ratios including TI, AR, RCMAXM1, RCMAXM2, RAUCM1 and RAUCM1 will be computed by Statistics and Programming.

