### 14.5.3. Reporting Standards for Pharmacokinetic

| Pharmacokinetic Concentration Data                              |   |
|---|---|
| PC Windows Non-Linear (WNL) File                                | 
PC WNL file (CSV format) for the non-compartmental analysis by Clinical Pharmacology Modelling and Simulation function will be created according to SOP_00000314000: Non-compartmental Analysis of Clinical Pharmacokinetic Data.
 
Note: Concentration values will be imputed as per GUI_51487.
   |
| ADPC data file  | 
To create ADPC the SDTM PC domain dataset will be merged with the Subject-Level Analysis Dataset (to get demographic information) and with SDTM EX domain (to get reference timepoint date).
 
Reference timepoint date will be populated for both study drug and active metabolite based on study treatment information from SDTM EX domain.
 
To populate analysis values in ADPC (AVAL(C)) adjustments to the PCSTRESN will be done based on imputation rules from "Non-Compartmental Analysis of Pharmacokinetic Data, CPMS Global" document.
 
Total Moiety parameter will be added, along with concentrations of study drug and active metabolite, and derived as the sum of study drug and active metabolite concentrations converted to nM units.
 |
| Descriptive Summary Statistics, Graphical Displays and Listings | 
Refer to IDSL PK Display Standards.
 
Refer to IDSL Statistical Principle 6.06.1.
 
Note: Concentration values will be imputed as per GUI_51487 for descriptive summary statistics/analysis and summarised graphical displays only. Assign zero to NQ values.
   |
| Pharmacokinetic Parameter Derivation                            |   |
| PK Parameters to be Derived by PK Programmer                    | The following PK parameters will be derived by the Programmer: $C_{max}$ , $T_{max}$ , and $C_{\tau}$ .   |
| Pharmacokinetic Parameter Data                                  |   |
| Is NQ impacted PK Parameters Rule Being Followed                | Yes. Refer to Standards for Handling NQ Impacted PK Parameters.   |

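### SAP Table 2 runs AUC(0-τ) to the next pre-dose, which is 72 h after Day 1 but 24 h on Day 15, so the accumulation ratio as written is too low

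*SAP*

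**What the plan says.** SAP Table 2 (section 9.1.2) describes AUC(0-τ) as "Area under the concentration-time curve from time zero to the predose of the next dose" and Cτ as the "observed concentration at the end of a dosing interval, immediately before the next administration". AR is AUC(0-τ) on Day 15 divided by AUC(0-τ) on Day 1. Time invariance (TI) has the same numerator over AUC(0-∞) on Day 1.

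The dosing schedule is in the protocol. In Table 2 of section 1.3, "no dose will be given on Day 2 or Day 3 of the first cycle". Section 8.6 says that Part 1 participants "will receive a single dose on Day 1 and then begin continuous dosing after collection of the 72 hour PK sample". For Day 15, the same section places the 24 h sample just ahead of the following dose.

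Of the late Day 1 samples, the protocol's Table 2 says: "The 48 hr and 72 hr timepoints could be removed with emerging data".

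The ratios, AR among them, "will be computed by Statistics and Programming". SAP section 14.5.3 opens its list of Cmax, Tmax and Cτ with "The following PK parameters will be derived by the Programmer".

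**The concern.** One definition is applied to two days on which the gap to the next dose differs threefold. Read as written, AR compares 24 h of exposure at steady state with 72 h of exposure after the first dose. Cτ compares a 24 h trough with a 72 h concentration. The two errors run in opposite directions: AR is pulled down, while any reading of the Day 15 trough against the Day 1 trough is pushed up.

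Both parameters are summarised by study day for the parent and both metabolites (SAP Tables 4.4 to 4.6), under the Part 1 secondary PK objective that the SAP retains. A reader could see almost no accumulation in AR and a large rise in trough in the same table. AR would also carry little information beyond TI. If the 48 h and 72 h samples were dropped, the Day 1 AUC(0-τ) as defined would have no observed end point.

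**Working it through.** **Inputs**

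- Day 1 interval to the next dose: 72 h (protocol Table 2 in section 1.3, and section 8.6).
- Day 15 interval to the next dose: 24 h (protocol section 8.6).
- Disposition: protocol section 2.2.1.5 says that concentration "declines bi-exponentially with a mean terminal elimination half-life of 20-24 hours".
- Observed Day 15 to Day 1 rise in mean AUC: up to 2 to 4 fold (same section; AUC interval not stated).

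The documents give no planned value of AR to reproduce.

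**Is τ set to 24 h for Day 1 anywhere?** Protocol section 9.6.3.1 ties the AUC to a dosing interval without giving its length. SAP section 9.1.3.1 offers AUC(0-24) as an alternative to AUC(0-τ), but only at steady state. SAP section 9.1.2 refers to current working practices and names no τ. So no passage sets it.

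**Direction.** On any Day 1 profile with measurable drug after 24 h, AUC(0-72) exceeds AUC(0-24). The literal AR is therefore lower than the equal-interval AR whatever the model.

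**Size, one compartment.** Let A(T) be the share of Day 1 AUC(0-∞) that falls in 0 to T hours: A(T) = 1 − 2^(−T/t½). With linear kinetics and steady state by Day 15, AUC(0-24) on Day 15 equals AUC(0-∞) on Day 1. Equal-interval AR is then 1/A(24) and literal AR is 1/A(72).

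| | t½ = 20 h | t½ = 24 h |
|---|---|---|
| A(24) | 0.5647 | 0.5000 |
| A(72) | 0.9175 | 0.8750 |
| A(72)/A(24) | 1.62 | 1.75 |
| AR on 24 h / 24 h | 1.77 | 2.00 |
| AR as written (24 h / 72 h) | 1.09 | 1.14 |
| Understatement, 1 − A(24)/A(72) | 38% | 43% |

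Summing over the actual schedule (Day 1, then daily from Day 4 to Day 15) gives the same AR values, so the steady-state assumption does no harm at these half-lives.

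**Size, bi-exponential.** The documents do not give the fast-phase share. I assumed that the fast phase holds f = 10% to 60% of the AUC with a half-life t_f of 2, 3, 4 or 6 h, and kept the terminal half-life at 20 or 24 h:

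A(T) = f(1 − 2^(−T/t_f)) + (1 − f)(1 − 2^(−T/t½)).

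- A(72)/A(24) runs from 1.17 (f = 60%, t_f = 2 h, t½ = 20 h) to 1.63 (f = 10%, t_f = 6 h, t½ = 24 h).
- The understatement is 15% to 39%.
- Equal-interval AR of 1.21 to 1.84 would be reported as 1.03 to 1.13.

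**Against the protocol's observed rise.** Suppose the 2 to 4 fold rise is a 24 h / 24 h ratio. The conversion factor depends only on the Day 1 profile. With the one-compartment factors the literal AR would be 2/1.75 = 1.14 to 4/1.62 = about 2.5. With the smallest bi-exponential factor the upper end is 4/1.17 = 3.4. If instead a single exponential must itself produce the 4-fold rise, then A(24) = 1/4, A(72) = 1 − 0.75³ = 0.578, and the literal AR is 1/0.578 = 1.73.

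**Overlap with TI.** AR/TI = AUC(0-∞)/AUC(0-τ), both on Day 1. With τ = 72 h this is 1/A(72) = 1.03 to 1.14 across both models. With τ = 24 h it is 1/A(24) = 1.21 to 2.00.

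**Trough.** One compartment: C(24)/C(72) on Day 1 = 2^(48/t½) = 5.28 at 20 h and 4.00 at 24 h. The bi-exponential grid reaches 8.9. A Day 15 to Day 1 trough ratio of 1.77 or 2.00 on 24 h values would read as 1.77 × 5.28 = 9.3 or 2.00 × 4.00 = 8.0.

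**The case against.** The best defence is that 24 h is plainly meant. The regimen is once daily, the 72 h gap after Day 1 is a PK washout rather than a dosing interval, and the SAP treats AUC(0-24) as interchangeable with AUC(0-τ) at steady state. Letting the late samples go while keeping AR also fits a 24 h Day 1 interval, and the 2 to 4 fold rise lies nearer a 24 h / 24 h ratio than the modelled literal value of 1.03 to 1.14. AUC(0-τ) itself comes from WinNonlin under a sponsor SOP, so a pharmacokineticist sets the interval; programming only forms the ratio. No Day 15 to Day 1 trough ratio is tabulated. AR is descriptive, Part 2 and the RP2D, population PK and PK/PD analyses are cancelled, and individual concentrations and parameters are listed, so a 24 h AR could be recomputed.

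Much of this stands. The error arises only if the definition is followed as written, the trough ratio is one a reader would have to form, and the consequence is limited to descriptive reporting. But the case for 24 h is inference, and it runs against an explicit end point in Table 2. For Cτ, which the programmer derives directly, no such intermediate step protects the result. A definition that is right only when the analyst departs from it should be corrected.

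**Conclusion.** The concern holds: AR and Day 1 Cτ are wrong as written. The downward direction for AR needs no model beyond measurable drug after 24 h. The size does: 38% to 43% too low with one compartment at the stated half-life, and 15% to 39% with an assumed fast phase. The AR values assume linear superposition and steady state by Day 15; the A(72)/A(24) factor and the AR/TI comparison rest on the Day 1 profile alone. TI is not affected, because its Day 1 term is AUC(0-∞) and its Day 15 term already covers 24 h. Since no test or dose decision in the SAP uses AR, this should be corrected before the PK tables are produced, but it does not threaten the study's main conclusions.

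**What to change.** In SAP Table 2, state that τ is 24 h on both Day 1 and Day 15. Write AR as AUC(0-24) on Day 15 over AUC(0-24) on Day 1 for the parent and both metabolites, and define Day 1 Cτ as the 24 h concentration. If the 72 h value is of interest, report it separately as C72h. Leave TI unchanged.

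The cost is two lines of SAP wording. The 24 h sample is already scheduled on both days, so no new data are needed, and AR no longer depends on whether the 48 h and 72 h samples are kept.

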### 9.1.3. Statistical Analysis of Pharmacokinetic Parameters

Plasma concentration-time data will be listed by dose, cohort and study day and summarized using descriptive statistics (n, mean, SD, median, minimum and maximum) by planned relative assessment time. Mean and/ or median values will be plotted over time. Individual plasma pharmacokinetic parameters values as well as a descriptive summary (mean, standard deviation, median, minimum, maximum, geometric mean, and the standard deviation, CV% and 95% confidence interval of log-transformed parameters (if applicable)) by dose, cohort and study day will be reported.

The following pharmacokinetic statistical analyses will only be performed, if sufficient data is available (i.e. if subjects have well defined plasma profiles).

#### 9.1.3.1. Dose Proportionality

Cmax and AUC (AUC(0-∞), single dose, and AUC(0-τ) or AUC(0-24), steady state), will be plotted as a function of the dose administered. Dose proportionality of AUC and Cmax for GSK3368715 following single dose administration and AUC(0-τ) or AUC(0-24) and Cmax following repeat dose administration will be assessed graphically and using the power model as described below:

$$\log(\text{pharmacokinetic parameter}) = a + b * \log(\text{dose})$$

where a is the intercept and b is the slope.

The power model will be fitted by restricted maximum likelihood (REML) using SAS Proc Mixed. Both the intercept and slope will be fitted as fixed effects. If there is sufficient data, the model may also be fit with the intercept and/or slope as random

effects depending on the ability of the model to converge and on estimation of variance-covariance matrix. The mean slope and corresponding 90% confidence interval will be estimated from the power model.

|  |
|--|
| Part 1 Dose Proportionality Analysis  |
| Endpoint(s)   |
| 
 
• Cmax and AUC (AUC(0-∞), single dose, and AUC(0-τ) or AUC(0-24), steady state)
 
   |
| Model Specification   |
| 
 
• Proc Mixed code for dose proportionality analysis:
 PROC MIXED data=pkpar;
 BY paramcd;
 CLASS subjid;
 MODEL logpk = logdose / ddfm=kr;
 RANDOM subjid;
 RUN;
 
 |
| Model Checking & Diagnostics  |
| 
 
• Refer to Appendix 10: Model Checking and Diagnostics for Statistical Analyses.
 
   |

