| 4.4                     | PK         | PK06                 | Summary of Derived GSK3368715 Pharmacokinetic Parameters by Dose Level, Cohort and Study Day | 
PK parameters: Cmax, Tmax, Ctrough, AUC0-t, AUC0-tau, AUCinf, t1/2, λz, TI and AR determined from the concentration-time data in ng/ml;
descriptive summaries: mean, SD, median, min, max, geometric mean & SD, CV%, and 95%CI of log-transformed parameters, if applicable.
 
Note: Separate 100mg dose by Dose Escalation, PK/PD and Combined (Dose Escalation and PK/PD) Cohorts.
                  | SAC         |
| 4.5                     | PK         | PK06                 | Summary of Derived GSK3963583 Pharmacokinetic Parameters by Dose Level, Cohort and Study Day | 
PK parameters: Cmax, Tmax, Ctrough, AUC0-t, AUC0-tau, AUCinf, t1/2, λz, TI, AR, RCMAXM1 and RAUCM1 determined from the concentration-time data in ng/ml;
descriptive summaries: mean, SD, median, min, max, geometric mean & SD, CV%, and 95%CI of log-transformed parameters, if applicable.
 
Note: Separate 100mg dose by Dose Escalation, PK/PD and Combined (Dose Escalation and PK/PD) Cohorts.
 | SAC         |

| Pharmacokinetic: Tables |            |                      |  |   |             |
|-------------------------|------------|----------------------|--|---|-------------|
| No.                     | Population | IDSL / Example Shell | Title  | Programming Notes   | Deliverable |
| 4.6                     | PK         | PK06                 | Summary of Derived GSK3983164 Pharmacokinetic Parameters by Dose Level, Cohort and Study Day | PK parameters: Cmax, Tmax, Ctrough, AUC0-t, AUC0-tau, AUCinf, t 1/2 , λz, Tl, AR, RCMAXM2 and RAUCM2 determined from the concentration-time data in ng/ml; descriptive summaries: mean, SD, median, min, max, geometric mean & SD, CV%, and 95%CI of log-transformed parameters, if applicable.
Note: Separate 100mg dose by Dose Escalation, PK/PD and Combined (Dose Escalation and PK/PD) Cohorts. | SAC         |
| 4.10                    | PK         |                      | Summary Results of Single Dose Proportionality Assessment Using Power Model for GSK3368715   |   | SAC         |

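### The PROC MIXED code in SAP 9.1.3.1 does not deliver the dose-proportionality analysis that its own text describes

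*SAP*

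**What the plan says.** SAP Section 9.1.3.1 describes a power model, log parameter on log dose, for two situations: single dose, and repeat dose ("following single dose administration and AUC(0-τ) or AUC(0-24) and Cmax following repeat dose administration will be assessed graphically" as well as by the model). Its endpoint box pairs AUC(0-∞) with single dose and AUC(0-τ) or AUC(0-24) with steady state. Cmax belongs to both.

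On model form, the text says "Both the intercept and slope will be fitted as fixed effects". It then adds an option: "If there is sufficient data, the model may also be fit with the intercept and/or slope as random" effects, subject to convergence and to estimation of the covariance matrix. On output, it says "The mean slope and corresponding 90% confidence interval will be estimated from the power model".

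The code under the model-specification heading reads a dataset called pkpar, runs by parameter code only, and has the model line "MODEL logpk = logdose / ddfm=kr" followed by "RANDOM subjid". It contains no study day, no WHERE statement, and no model option other than the degrees-of-freedom method. The SAP does not define pkpar.

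In the display list (SAP Section 14.10.6), the only power-model table is 4.10, "Summary Results of Single Dose Proportionality Assessment Using Power Model for GSK3368715".

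**The concern.** The text and the code in one section specify different analyses, and the code carries the model-specification label. A programmer who runs it as printed gets no slope and no 90% CI, and may fit both study days together. A programmer who repairs it must choose between models without a recorded rule. Characterising PK is a secondary objective that survives the early stop, and this is the only model-based PK analysis left, since population PK and PK/PD modelling have been dropped (SAP Sections 11 and 12).

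**Working it through.** The plan states no figure to reproduce. The check sets code against text and then asks what each mismatch does.

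**1. Output.** Without SOLUTION or an ESTIMATE statement, PROC MIXED prints the F test for log dose but no slope and no interval. Adding CL alone would give the default 95% limits. For scale, take the 19 participants dosed by Amendment 3 (Protocol Section 2.2.1.4.3; no final count is given), so df = 19 − 2 = 17. The ratio of t quantiles is 2.110 / 1.740 = 1.213, so a default interval would be 21% wider than the stated one. This gap does not depend on how pkpar is built.

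**2. Which parameters exist on both days.** SAP Table 2 computes AUC(0-∞) on Day 1 only. It needs AUC(0-τ) on Days 1 and 15 for the accumulation ratio. Section 9.1.3 summarises parameters by study day. Under the stated endpoints, only Cmax is certain to carry the same name on both days. AUC(0-τ) joins it if its Day 1 values stay in pkpar.

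**3. What pooling would do.** Dose is constant within a participant, because SAP Section 5.2 reports by the dose first received. Let the day-specific slopes be b1 and b15, the shift between days δ = ln(accumulation), the subject variance σs² and the residual variance σe².

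- *Slope.* If everyone has both days, the pooled slope is the slope of participant means, with expectation (b1 + b15)/2. Equal slopes give no bias. With assumed slopes of 1.0 and 1.3 it is (1.0 + 1.3)/2 = 1.15, which is neither.
- *Interval.* With no day term, δ falls into the residual. For equal slopes the expected mean squares are 2σs² + σe² between participants and σe² + δ²/2 within. When δ²/2 exceeds 2σs², the subject variance tends to be estimated as zero.
- *Illustration.* Assume 19 participants split 3/9/7 over 50/100/200 mg, 70% of log variance between subjects, and equal slopes. At CV 30%, log variance is ln(1.09) = 0.0862 and 2σs² = 2 × 0.7 × 0.0862 = 0.121. For 2- and 4-fold accumulation, δ²/2 is 0.240 and 0.961. In 3,000 simulated trials per setting, the subject variance was zero in 96% and 100%. The mean 90% half-width was 0.261 and 0.437, against 0.241 and 0.239 for Day 1 alone, ratios of 1.08 and 1.83. At CV 70% the ratios were 0.478/0.515 = 0.93 and 0.539/0.517 = 1.04. A model with a day term would give about √(0.7 + 0.3/2) = 0.92, so here the pooled interval runs from about right to nearly twice too wide.

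The accumulation range is borrowed from the Protocol's statement on AUC (Section 2.2.1.5: "mean AUC was up to 2-4 fold higher on Day 15 as compared to Day 1 in all dose groups"). No Cmax accumulation is given, so this shows a mechanism, not an expected size.

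**4. One record per participant.** With one day only, and always for AUC(0-∞), the covariance matrix is (σs² + σe²)I, so only the sum is identified. In one simulated dataset of 19, −2 REML log-likelihood was −25.819015 whether 0, 25, 50, 75 or 100% of the variance was assigned to subject. The slope (0.750) and SE (0.119) did not change and the slope equalled ordinary least squares. The cost is convergence or covariance warnings and unreliable Kenward-Roger degrees of freedom, not a wrong slope.

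**5. Displays.** The text promises single-dose and repeat-dose assessments. The list has a table for the first only.

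**The case against.** The strongest reply is that the text already settles most of this. It separates the two dosing situations, ties each AUC to one of them, and makes random effects conditional on sufficient data and convergence. Table 4.10 is a single-dose table, which suggests a Day 1 subset. On this view the snippet shows an optional variant, and SOLUTION, CL and ALPHA are output options that any programmer would add at first run. No hypothesis is tested, enrolment has ended, and the analysis runs only if data suffice.

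Much of this stands. It makes pooling conditional rather than certain, and it lowers the importance. It does not remove the mismatch. The SAP never says that pkpar is filtered or that parameter codes are day-specific, the code does not mark its random effect as optional, and a Day 1 subset is exactly where that term cannot be estimated. Nor does it explain the missing repeat-dose table.

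A reader might go further and infer that the code certainly mixes days, that it biases the slope downward because Day 15 profiles are lost more often at higher doses, or that every fit would be invalid. The documents do not support these readings. Pooling depends on an undefined dataset. No dose-related Day 15 loss rates and no final split of participants by dose are given, and the accumulation figure is for AUC. With one record per participant, the slope and SE are unaffected.

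**Conclusion.** The point holds as a mismatch between text and code, of minor severity. Three elements follow directly from the page: no slope or 90% CI is requested, the random effect is unconditional although the text makes it optional, and no repeat-dose power-model table is listed. A fourth, pooling of Day 1 and Day 15, holds unless pkpar is filtered first. It concerns Cmax, and AUC(0-τ) only if Day 1 values are kept.

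No bias size can be stated from the documents. The interval ratios above rest on an assumed dose split, assumed variances and equal slopes. If the slopes differ, or Day 15 profiles are lost in a dose-related way, a pooled slope describes neither single dose nor steady state. The effect is confined to a descriptive secondary PK analysis.

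**What to change.** In SAP Section 9.1.3.1:

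- Restrict pkpar to the stated endpoint and day pairs: Day 1 for AUC(0-∞) and Cmax; Day 15 for AUC(0-τ) or AUC(0-24) and Cmax. State this in the text.
- Run the model by parameter code and study day.
- Omit the subject random effect when there is one record per participant.
- Use `MODEL logpk = logdose / SOLUTION CL ALPHA=0.1 DDFM=KR;`.

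In SAP Section 14.10.6, add a repeat-dose (Day 15) power-model table beside Table 4.10.

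The cost is a few lines of SAP code and one more table. No new data are needed.
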